11.4.3.5. Vital Sign Analyses

Descriptive statistics will be provided for the vital signs measurements by scheduled time of evaluation and by treatment group for the Safety Analysis Set, as well as for the change from baseline in the Main Treatment Period. The baseline value is defined as the last non-missing value before the initial administration of study treatment.

Similar summaries will also be provided for vital signs by scheduled time of evaluation during the Extension Period, as well as for the change from Month 3 Visit to the visits after Month 3.

11.4.4. Other Endpoint Analysis

Descriptive statistics for QOL score at baseline and Month 3 will be summarized for each question, each dimension, and overall by treatment group and QOL specified age group for Safety Analysis Set.

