2.1.3. Exploratory Objectives

The exploratory objectives are:

- To assess the quality of life (QOL) using validated questionnaires.
- To compare the intra-patient safety (Investigator reported bleeding) and efficacy (Investigator reported TE) during the Main Treatment Period compared with the prior treatment occurring within 3 months of randomization.
- To compare edoxaban regimen with available existing historical data based on literature review and search for registered clinical trials with similar endpoints.
- To analyze the primary prevention and secondary prevention of TE.

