6.3. Randomization (Day 1, Visit 2)

Investigators will maintain a confidential subject identification code list of names of all subjects randomized to study to allow the Investigator to reveal the identity of any subject when necessary. If all procedures and tests done before randomization confirm the subject's eligibility (Section 6.2) for the study, then the IXRS will be contacted to randomize the subject.

Urine pregnancy test in females of childbearing potential by definition are those females that have reached menarche and until becoming postmenopausal unless permanently sterile (defined as no menses for 12 months without an alternative medical cause).

Randomization may occur in IXRS the day prior to dosing for clinical logistics. Screening Visit and Randomization Visit may occur on the same day. The first dose of study treatment may occur on Day 1 or Day 2 (see Section 5.2.4)

The following activities should be done at the time of randomization.

NOTE: For therapeutic monitoring of SOC the Investigator will use discretion to decide when and how often to repeat INR or anti-FXa levels or aPTT measurements after randomization. These measurements will be taken and evaluated in the clinic, or alternatively, an optional site-specific local laboratory.

NOTE: For subjects randomized to the edoxaban arm, a blood sample will be collected before the first dose of edoxaban for PD analysis only if the subject did not receive any heparin (UFH or LMWH) or VKA 24 hours prior to randomization.

- PD blood sample for subjects randomized to edoxaban taken before dosing that day
- Discretionary anti-FXa level and/or aPTT measurement for subjects on SOC with heparin and INR assessment for the subjects on SOC with VKA
- Record any prior and/or concomitant medications used since the last visit.
- Record any AEs since screening visit, including any bleeding events.
- Urine pregnancy test (for post-menarchal females)
- Physical examination for body weight only
- Dispense study drug and record amount (number of tablets/bottles) dispensed. Prescription based, locally sourced SOC study therapy will need to be supported by a prescription identifying the type of SOC to be provided;
- Explain the study drugs and the proper daily dosing to the parent(s) or guardian(s) and subject (if applicable) using the study drug dosing calendar, and confirm that the subject understands the proper daily dosing of study drug.

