- Instruct subject to bring all medications including study drug packaging and bottles to each visit (monthly visits even if there are no scheduled procedures).
- Complete the QOL Questionnaire. Note the QOL can be filled out by EITHER a parent or the study participant. The same person should complete the QOL at Month 3.

Parent(s) or guardian(s) or legally acceptable representative parent(s) or guardian(s) and subject (if applicable) will be provided with information detailing symptoms suggestive of bleeding and TE. Parent(s), guardian(s) or subject will be asked to immediately contact the Investigator if these symptoms occur.

The following information may be provided to the parent(s), guardian(s) or subject (information booklet):

- The local medical contact person and emergency telephone number
- The visit schedule
- How to recognize and report signs and symptoms of possible bleeding and thromboembolic events (see Section 7.1 and Section 9.1).
- How to use the study drugs and instructions to keep empty medication packages

- Blood collections for assessing the INR will be dependent on the discretion of the Investigator.
- Provide subjects with a subject identification safety card and a prohibited medication card

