10. OTHER ASSESSMENTS

A pediatric QOL questionnaire will be issued at randomization and at the end of the treatment period (Month 3, Visit 5) to assess such categories as: health and activities, feelings about themselves, relationships with others, and school behavior. Note the QOL can be filled out by EITHER a parent or the study participant. The same person should complete the QOL at Month 3.

PedsQL version 4.0, generic core scale will be used in the study. The Sponsor will provide a hard copy of the questionnaire. Data will be entered into the EDC.

The following questionnaires will be used:

- Adolescent (13-18) Self report
- Adolescent (13-18) Parent report
- Child (8-12) Self report
- Child (8-12) Parent report
- Young child (5-7) Self report
- Young child (5-7) Parent report
- Toddler (2-4) Parent report

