^f Targeted physical examination performed by an Investigator or other healthcare professional designated by the Investigator. Vital signs include blood pressure, heart rate, and body temperature after resting in a sitting or supine position [Note: the appropriate cuff size base on arm circumference will be used.] see Section 9.9). Height and body weight (may be performed by an Investigator or other healthcare provider designated by the Investigator).

^g Hepatitis serology will be performed if a combination of LFT and TBL abnormalities which define Hy's Law cases as ALT and/or AST \geq 3 × ULN with TBL \geq 2 × ULN.

^h aPTT and INR assessment will be done for all subjects at local laboratory.

- ⁱ Discretionary anti-FXa levels assessments and/or aPTT measurements will be performed locally for the subjects on SOC with heparin (UFH or LMWH) and INR assessments will be performed locally for the subject on SOC with VKA. Additional interim unscheduled visits may be performed at the Investigator's discretion to assess VKA therapeutic levels (2-3) based on INR and to assess LMWH or UFH therapeutic blood levels based anti-FXa activity (and/or) aPTT.
- ^j Note: Valid screening echocardiograms are images taken within 5 weeks prior to Randomization Visit. A Month 3 echocardiogram is optional if the subject experiences a symptomatic TE documented by an image. A reported post-Month 3 symptomatic TE should have a supporting appropriate image. If no symptomatic TE is reported during the Extension Period, the Investigator has the option to perform an echocardiogram at his/her discretion to rule out any asymptomatic TE event at study discontinuation.
- ^k Highly sensitive urine pregnancy test to be performed for females of childbearing potential.
- ¹ Only the parent or study participant will fill out the form. The same person will fill out the QOL questionnaire at the Screening Visit and Month 3.
- ^m AE/SAE reporting should occur throughout the study and not be restricted to specific visits.
- ⁿ Symptomatic endpoint events should be reported as soon as site personnel learn of the event. Symptomatic endpoint event surveillance with supporting imaging should occur throughout the study and not be restricted to specific visits.
- ^o Only for subjects receiving edoxaban. In addition, one sample will be taken at for every AE classified as a TE, or major or CRNM bleeding. PK samples will be collected pre-dose and 1 to 3 hours post-dose.

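### Section 11.4.4 plans no baseline-adjusted PedsQL difference and no split by respondent, and the protocol contradicts itself on when the baseline form is completed

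*Combined protocol and SAP*

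**What the plan says.** Quality of life is an exploratory objective: "To assess the quality of life (QOL) using validated questionnaires" (Section 2.1.3). The instrument is PedsQL 4.0, given at the start and at Month 3. The whole analysis plan is one sentence in Section 11.4.4: "Descriptive statistics for QOL score at baseline and Month 3 will be summarized for each question, each dimension, and overall by treatment group", with a further split by "QOL specified age group for Safety Analysis Set".

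On the respondent, Section 6.3 says: "Note the QOL can be filled out by EITHER a parent or the study participant". It adds: "The same person should complete the QOL at Month 3". Sections 2.3.5 and 10 list separate self and parent forms for ages 5-7, 8-12 and 13-18. The youngest band has only "Toddler (2-4) Parent report", and no form is listed below age 2.

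On timing, Sections 2.3.5, 6.3 and 10 and the Table 17.1 grid place the first form at randomization. Footnote l to the same table says: "The same person will fill out the QOL questionnaire at the Screening Visit and Month 3". Section 6.3 describes the allocation step (if eligibility is confirmed, "then the IXRS will be contacted to randomize the subject") and then lists the visit activities, with the questionnaire as the last item. It states no order between the form and the disclosure of the arm.

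**The concern.** Each child with both forms supplies a baseline and a follow-up score, but the plan never links the two. Laboratory values and vital signs (Sections 11.4.3.4 and 11.4.3.5) do get a change from baseline. For quality of life a reader will see two sets of means per arm, split by age group, with no estimate of the difference and no measure of its uncertainty. Within three of the four age bands the planned table gives no way to tell parent from self reports.

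The timing matters because the trial is open-label. If a family knows its arm before answering, the baseline answers may reflect that knowledge, and any later analysis that uses the baseline inherits the problem. An analysis can still be added before database lock. A baseline form completed too late cannot be repeated.

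**Working it through.** **Plan's own figure.** The documents give no precision or power figure for quality of life. The only sample-size figure (Section 11.6) is the 95% CI for the bleeding risk difference, from 8.5% and 10.3% with 100 and 50 subjects. SE = √(0.085×0.915/100 + 0.103×0.897/50) = 0.0512. Then −0.018 ± 1.96×0.0512 gives −11.8% to 8.2%, as stated. This confirms the arm sizes used below and says nothing about PedsQL.

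**Inputs.** Arm sizes of 100 and 50 come from Section 11.6. The baseline to Month 3 correlation ρ is not in the documents and is assumed at 0.3, 0.5 and 0.7. Scores are in SD units, with complete data.

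**Precision of the Month 3 difference.**
- Raw: SE = √(1/100 + 1/50) = 0.1732, so the 95% half-width is 1.96×0.1732 = 0.339 SD.
- ANCOVA: multiply the half-width by √(1−ρ²).
- Change score: multiply it by √(2(1−ρ)).

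| ρ (assumed) | Raw half-width | ANCOVA | Change score | Raw variance ÷ ANCOVA variance = 1/(1−ρ²) |
|---|---|---|---|---|
| 0.3 | 0.339 | 0.324 | 0.402 | 1/0.91 = 1.10 |
| 0.5 | 0.339 | 0.294 | 0.339 | 1/0.75 = 1.33 |
| 0.7 | 0.339 | 0.242 | 0.263 | 1/0.51 = 1.96 |

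A change score is worse than the raw comparison at ρ = 0.3 and no better at 0.5, so adding change from baseline alone would not be a safe remedy.

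Fewer than 150 will contribute, because no form is listed below age 2 and missing data are generally not imputed (Section 11.1). With an illustrative 80 versus 40, the raw half-width is 0.380 SD and ANCOVA gives 0.362, 0.329 and 0.271 SD. The variance ratios do not change.

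**Effect of a baseline form answered after allocation.** Suppose knowledge of the arm shifted one arm's baseline by 0.1 to 0.3 SD (assumed).
- A change score would be biased by the whole shift, 0.1 to 0.3 SD.
- ANCOVA would be biased by ρ times the shift, from 0.3×0.1 = 0.03 to 0.7×0.3 = 0.21 SD.
- The raw Month 3 contrast does not use the baseline, so its bias from this source is zero.

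**Respondent mix.** With an assumed parent-child gap of 0.2 to 0.4 SD and a 10 to 20 point difference between arms in the share of parent reports, the contrast moves by 0.2×0.1 = 0.02 to 0.4×0.2 = 0.08 SD.

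**Which baseline rule applies.** Section 11.1 has two rules: last value before randomization for efficacy variables, last value before first dose for safety variables. Quality of life is assigned to neither. A form completed between allocation and first dose would satisfy the second rule and fail the first.

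**The case against.** The strongest reply is that no comparison was promised. The objective is exploratory and says assess, where neighbouring exploratory objectives say compare. Section 11.6 disclaims power, and Section 11.7 leaves detailed methods to an SAP whose text is not part of what was reviewed. Descriptive tables fit that objective. This stands as a limit on the weight of the point. It does not remove the point, because Section 11.1 already provides for descriptive 95% CIs and the proposal is one more of them.

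Three stronger readings are tempting, and the documents do not support them.
- **Parent and child reports will be pooled.** Section 11.4.4 does not say so; it is silent on respondent. The same-person rule also limits mixing within a subject, though it does not balance respondents between arms.
- **The baseline form follows allocation and dispensing.** Its place in the Section 6.3 list does not show this. The list is not chronological: the pregnancy test, needed for eligibility, comes after a blood sample described for subjects already randomized to edoxaban. Footnote l points to Screening. What can be shown is a contradiction and a missing requirement.
- **No unbiased comparison is possible.** Month 3 scores by arm do not use the baseline form, and chance baseline imbalance in a randomized trial costs precision rather than creating bias.

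It is also fair to say that the gain depends on an assumed correlation. At 0.3 it is only about 1.1 times.

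**Conclusion.** The point holds as a modest one. Section 11.4.4 names no between-arm difference, CI, baseline-adjusted estimate or respondent split for PedsQL. The documents disagree on when the baseline form is completed, and nothing requires it to precede knowledge of the arm.

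Omitting the adjustment leaves the variance of the arm difference about 1.1 to 2.0 times what ANCOVA would give. That rests on an assumed correlation of 0.3 to 0.7, 100 versus 50 subjects and complete data. The loss is one of precision, and the timing of the baseline form does not bias the raw Month 3 comparison. Open-label self-report, the as-treated analysis set and missing forms remain as separate limits that this change does not remove.

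Only an exploratory objective is affected. The primary bleeding analysis and the sample size are untouched.

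**What to change.** (a) In Section 6.3, require the baseline form to be completed before the IXRS allocation is disclosed. Reconcile footnote l of Table 17.1 with the grid and with Sections 2.3.5, 6.3 and 10, so that all name the same visit. A form completed before allocation satisfies both baseline rules in Section 11.1.

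(b) In Section 11.4.4, add a descriptive ANCOVA of the Month 3 total score on arm, adjusted for baseline score, respondent (parent or self) and age form, and report the difference with its 95% CI. Tabulate scores by respondent as well as by age group.

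The two parts belong together, because ANCOVA carries over ρ times any shift that knowledge of the arm puts into the baseline. The cost is one extra analysis of data already being collected (the form version identifies the respondent type) and a change of order at Visit 2.

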11.5. Interim Assessment

No formal statistical interim analysis is planned. However, an interim assessment by the IDMC of safety endpoints of the study will take place after the first 50 subjects in the edoxaban treatment group and 25 subjects in the SOC arm from 1 to <18 year of age complete the first 3 months of treatment. This will allow for enrollment of subjects <1 year of age.

11.6. Sample Size Determination

A sample size of 150 subjects was chosen for this study. This study is not a powered study intended to draw conclusions based on statistically significant differences between edoxaban and SOC. An adequately powered study would be unachievable due to the significantly large sample size required and the enormous challenge to enroll these pediatric patients. Although the sample size is not based on statistical consideration, assuming major and CRNM bleeding event rates (which are the primary endpoints for this study) are the same as observed in adult Hokusai-VTE Study, (ie, 8.5% and 10.3% in edoxaban and SOC arms, respectively); with 100 subjects in edoxaban arm and 50 subjects in standard of care arm, the 95% CI around the point estimate of the risk difference between edoxaban and SOC is -11.8%, 8.2%..

11.7. Statistical Analysis Process

The clinical study will be analyzed by the Sponsor or its agent/CRO.

The statistical analysis plan (SAP) will provide the statistical methods and definitions for the analysis of the efficacy and safety data, as well as describe the approaches to be taken for

summarizing other clinical study information such as subject disposition, demographic and baseline characteristics, study drug exposure, and prior and concomitant medications. The SAP will also include a description of how missing, unused, and spurious data will be addressed.

To preserve the integrity of the statistical analysis and clinical study conclusions, the SAP will be finalized prior to database lock.

All statistical analyses will be performed using SAS® Version 9.2 or higher (SAS Institute, Cary, NC 27513).

12. DATA INTEGRITY AND QUALITY ASSURANCE

12.1. Monitoring and Inspections

The Sponsor or designee's Medical Monitor and regulatory authority inspectors are responsible for contacting and visiting the Investigator for the purpose of inspecting the facilities and, upon request, inspecting the various records of the study (eg, CRFs, source data, and other pertinent documents).

The verification of adherence to the protocol; completeness, accuracy, and consistency of the data; and adherence to International Council for Harmonization (ICH) Good Clinical Practice (GCP) and local regulations on the conduct of clinical research will be accomplished through a combination of onsite visits by the monitor and review of study data remotely. The frequency of the monitoring visit will vary based on the activity at each clinical site. The monitor is responsible for inspecting the CRFs and ensuring completeness of the study essential documents. The monitor should have access to subject medical records and other study-related records needed to verify the entries on the CRFs. Detailed information is provided in the monitoring plan.

The monitor will communicate deviations from the protocol, SOPs, GCP and applicable regulations to the Investigator and will ensure that appropriate action (s) designed to prevent recurrence of the detected deviations is taken and documented.

The Investigator agrees to cooperate with the monitor to ensure that any problems detected in the course of these monitoring visits are addressed to the satisfaction of the Sponsor and documented.

In accordance with ICH GCP and the Sponsor's audit plans, this study may be selected for audit by representatives from the Sponsor. Audit of clinical site facilities (eg, pharmacy, drug storage areas, laboratories) and review of study related records will occur in order to evaluate the study conduct and compliance with the protocol, ICH GCP, and applicable regulatory requirements. The Investigator should respond to audit findings. In the event that a regulatory authority informs the Investigator that it intends to conduct an inspection, the Sponsor shall be notified immediately.

12.2. Data Collection

This study employs EDC. The eCRF should be kept current to enable the monitor to review the subject's status throughout the course of the study. The eCRF will be completed, reviewed, and electronically signed by the Investigator. Guidelines will be provided to facilitate data entry in the EDC modules.

All written information, study notes, and other material to be used by subjects and investigative staff must use vocabulary and language that are clearly understood as source documentation.

12.3. Data Management

Each subject will be identified in the database by a unique subject identifier as defined by the Sponsor.

To ensure the quality of clinical data across all subjects and clinical sites, a Clinical Data Management review will be performed on subject data according to specifications given by the Sponsor or designee's. Data will be vetted both electronically and manually for CRFs and the data will be electronically vetted by programmed data rules within the application. Queries generated by rules and raised by reviewers will be generated within the EDC application. During this review, subject data will be checked for consistency, completeness and any apparent discrepancies.

Data received from external sources such as central laboratories will be reconciled to the clinical database.

SAEs in the clinical database will be reconciled with the safety database.

All medical history entries (except terms pre-specified on the eCRF) and adverse events will be coded using Medical Dictionary for Regulatory Activities. All prior and concomitant medications will be coded using World Health Organization Drug Dictionary.

12.4. Study Documentation and Storage

The Investigator will maintain a Signature List of appropriately qualified persons to whom he/she has delegated study duties. All persons authorized to make entries and/or corrections on electronic CRFs will be included on the Signature List.

Investigators will maintain a confidential screening log of all potential study candidates that includes limited information of the subjects, date and outcome of screening process.

Investigators will be expected to maintain an Enrollment Log of all subjects enrolled in the study indicating their assigned study number.

Investigators will maintain a confidential subject identification code list. This confidential list of names of all subjects allocated to study numbers on enrolling in the study allows the Investigator to reveal the identity of any subject when necessary.

Source documents are original documents, data, and records from which the subject's CRF data are obtained. These include but are not limited to hospital records, clinical and office charts, laboratory and pharmacy records, diaries, microfiches, X-rays, and correspondence.

Records of subjects, source documents, monitoring visit logs, data correction forms, CRFs, inventory of study drug, regulatory documents (eg, protocol and amendments, IRB/EC correspondence and approvals, approved and signed ICFs, Investigator's Agreement, clinical supplies receipts, distribution and return records), and other Sponsor correspondence pertaining to the study must be kept in appropriate study files at the clinical site (Trial Master File). Source documents include all recordings and observations or notations of clinical activities and all reports and records necessary for the evaluation and reconstruction of the clinical study. These records will be retained in a secure file for the period required by the institution or clinical site policy. Prior to transfer or destruction of these records, the Sponsor must be notified in writing and be given the opportunity to further store such records.

